13.7.2.2. Handling of Missing Data for Statistical Analysis

Element	Reporting Detail
Snapshot	
• In the Snapshot dataset, subjects without HIV – 1 RNA data in the assessment window for the visit of interest (due to missing data or discontinuation of IP prior to the visit window) do not belong to 'HIV-1< 50 c/mL (or 200 c/mL) The nature of this missing data will be further classified in Snapshot summaries as either 'HIV-1 RNA≥50' or 'No Virologic Data at Week X';• See Appendix 9: Snapshot Algorithm Details
LOCF (COVID-19 Related)	
• Missing HIV-1 RNA values within an analysis visit for reasons related to COVID-19 will be imputed using the last on-treatment value from earlier analysis timepoints.• This approach will be used in the primary snapshot analysis to address missing data due to COVID-19.

13.8. Appendix 8: Values of Potential Clinical Importance

ECG values of potential clinical importance are defined as QTc > 500 msec or increase from baseline in QTc \geq 60 msec.

13.9. Appendix 9: Snapshot Algorithm Details

Detailed Algorithm Steps

 Consider an analysis visit window for Month X as defined in Table 2. The HIV-1 RNA threshold of 50 will be analysed, in this study The COVID-19 pandemic presents significant logistical challenges for many clinical sites around the world, with variable restrictions being placed on site resources and operations, and on an individual participants ability to attend clinic visits. The snapshot algorithm is modified to allow for the presentation of full scope of COVID-19 relatedness. The analysis window for 'Month 12' and HIV-1 RNA threshold of '50 c/mL' are used for the purpose of illustration. A participant's Snapshot response and reason at Month 12 are categorized as below. 
 HIV-1 RNA < 50 c/mL HIV-1 RNA \geq 50 c/mL 
 Data in window not below 50 
 Non-COVID-19 related 
 Discontinued for lack of efficacy Discontinued for other reason while not below 50 COVID-19 related 
 Discontinued for lack of efficacy Discontinued for other reason while not below 50 No Virologic Data at Month 12 Window 
 Non-COVID-19 related 
 Discontinued study due to AE or death Discontinued study for other reasons On study but missing data in window COVID-19 related 
 Discontinued study due to AE or death Discontinued study for other reasons On study but missing data in window Change in background therapy*

* Note: Use of CAB + RPV oral bridging and SOC oral bridging medication, where the latter is due to unavailability of CAB/RPV IM injections or oral CAB+RPV during the pandemic, will not be considered a "Change in background therapy" in the Snapshot algorithm. All other permanent changes in ART are not permitted in this protocol.

- The steps in determining response and reasons are indicated in the table below, in the order stated.
- Background therapy is not given to participants while on study. The “change in background therapy” in detailed steps below refers to the “change in ART” in this study.

Detailed steps		
Condition ('Month 12' indicates Month 12 window)	Response	Reasons
1. If non-permitted change in background therapy prior to Month 12	HIV-1 RNA \geq 50	Change in background therapy
2. If non-permitted change in background therapy during Month 12 
 Last on-treatment VL during Month 12 prior to/on the date of change \geq 50 c/mL 	HIV-1 RNA \geq 50	Data in window not below 50

 Last on-treatment VL during Month 12 prior to/on the date of change $<$ 50 c/mL 	HIV-1 RNA $<$ 50	

 No VL during Month 12 prior to/on the date of change 	HIV-1 RNA \geq 50	Change in background therapy
3. If none of the above conditions met		
3.1. On-treatment VL available during Month 12 
 Last on-treatment VL during Month 12 \geq 50 c/mL Last on-treatment VL during Month 12 $<$ 50 c/mL 	HIV-1 RNA \geq 50 HIV-1 RNA $<$ 50	Data in window not below 50
3.2. No on-treatment VL during Month 12		
3.2.1. If participants are still on study, i.e. a participant has not permanently discontinued the study treatment yet, or if a participant permanently discontinued the study treatment and the upper bound of analysis snapshot window is prior to the following date: 
 Min[max(Date of last injection + 35, Date of Last Dose of Oral Study Treatment (CAB+RPV, SOC Bridging) + 1), LTFU ART Start Date] 		

3.2.1.1. If no on-treatment VL during Month 12 is not due to COVID-19	No virologic data at Month 12 Window	On study but missing data in window (Non-COVID-19 related)	
3.2.1.2. If no on-treatment VL during Month 12 is due to COVID-19	No virologic data at Month 12 Window	On study but missing data in window (COVID-19 related)	
3.2.2. If participants withdraw before/during Month 12 due to			
3.2.2.1. Non-COVID-19 related safety reasons (e.g. AE/death, liver chemistry stopping criteria, renal toxicity withdrawal criteria, QTc withdrawal criteria etc., as recorded in eCRF Conclusion form)	No virologic data at Month 12 Window	Disc due to AE/death (Non-COVID-19 related)	
3.2.2.2. COVID-19 related safety reasons (e.g. AE/death, liver chemistry stopping criteria, renal toxicity withdrawal criteria, QTc withdrawal criteria etc., as recorded in eCRF Conclusion form)	No virologic data at Month 12 Window	Disc due to AE/death (COVID-19 related)	
3.2.2.3. Non-safety and Non-COVID-19 related reasons (e.g. Lack of efficacy, protocol deviation, withdrew consent, loss to follow-up, study closed/terminated, investigator discretion etc., as recorded in eCRF Treatment Discontinuation Form)			
○ Last on-treatment VL <50 c/mL OR no on-treatment VL available during study	No virologic Data at Month 12 Window	Disc for other reasons (Non-COVID-19 related)	
○ Last on-treatment VL \geq 50 c/mL AND withdrawal due to Lack of efficacy	HIV-1 RNA \geq 50	Disc. for lack of efficacy (Non-COVID-19 related)	
○ Last on-treatment VL \geq 50 c/mL AND withdrawal due to all other non-safety related reasons	HIV-1 RNA \geq 50	Disc. for other reason while not below 50 (Non-COVID-19 related)	
3.2.2.4. Non-safety and COVID-19 related reasons (e.g. protocol deviation, withdrew consent, loss to follow-up, study			

closed/terminated, investigator discretion etc., as recorded in eCRF Conclusion Form)			
○ Last on-treatment VL <50 c/mL OR no on-treatment VL available during study	No virologic Data at Month 12 Window	Disc for other reasons (COVID-19 related)	
○ Last on-treatment VL \geq 50 c/mL AND withdrawal due to Lack of efficacy	HIV-1 RNA \geq 50	Disc. for lack of efficacy (COVID-19 related)	
○ Last on-treatment VL \geq 50 c/mL AND withdrawal due to all other non-safety related reasons	HIV-1 RNA \geq 50	Disc. for other reason while not below 50 (COVID-19 related)	
a. Excluding permitted change in background therapy where change or decision to change is made prior to/on the first on-treatment viral result			
Examples from FDA guidance			
Data in Window			
Virologic outcome should be determined by the last available measurement while the patient is on treatment and continued on trial within the time window:			

 • HIV-1 RNA = 580 c/mL at Day 336, HIV-1 RNA below 50 c/mL on Day 350. This should be categorized as HIV-1 RNA below 50 c/mL. 			
No Data in Window			
Discontinued study due to Adverse Event or Death:			

 • Any patient who discontinues because of an AE or death before the window should be classified as Discontinued due to AE or Death (as appropriate), regardless of the HIV-1 RNA result, even if the HIV-1 RNA is below 50 c/mL at the time of discontinuation. • However, if a patient has an HIV-1 RNA value in the time window and also discontinues in the time window, the viral load data should be used to classify the patient's response. This is the Virology First hierarchy: 
 a. HIV-1 RNA below 50 c/mL at Day 336 and discontinues because of AE or even dies on Day 360 — this person is categorized as having HIV-1 RNA below 50 c/mL. b. HIV-1 RNA is 552 c/mL on Day 336 and the patient discontinues on Day 360, the patient is categorized as having HIV-1 RNA \geq 50 c/mL. 			
Discontinued for Other Reasons:			

 • Only patients who have achieved virologic suppression can be counted as Discontinued for Other Reasons. • If a patient discontinues the study before the time window because of lack of efficacy, then the patient should be included in the HIV-1 RNA \geq 50 row and not in the Discontinued for Other Reasons row. 			

Detailed Algorithm Steps

- If a patient discontinues because *participant withdrew consent* and his or her HIV-1 RNA result at the time of discontinuation was equal to or above 50 c/mL, then he or she should be categorized as HIV-1 RNA ≥ 50 and NOT as Discontinued for Other Reasons.
- If a patient discontinued because of *Lost to Follow-Up* and the last HIV-1 RNA result was 49 c/mL, then the patient can be categorized as Discontinued for Other Reasons.
- If patients changed background treatment — *not permitted by protocol*— they should be considered an efficacy failure and captured in the HIV-1 RNA ≥ 50 c/mL row.

On study but missing data in window:

- If there are no data during Days 294 to 377, but there is an HIV-1 RNA below 50 c/mL on Day 380, this patient should be considered *On Study but Missing Data in Window*.
- If there are no data during Days 294 to 377, but there is an HIV-1 RNA equal to or above 50 c/mL on Day 280, this patient also should be classified as *On Study but Missing Data in Window*.

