Staff Study Participant Questionnaire		X ^a				X ^b						X ^b
Staff Study Participant Interviews (SSI)		X ^a				X ^b						X ^b
Staff Study Participant Monthly Facilitation Calls ^c		X	X	X	X	X	X	X	X	X	X	

- a. Questionnaire and interview should be conducted prior to the first patient receiving their first CAB + RPV LA injection at that site.
- b. Questionnaire and interview should be conducted within approximately 4 weeks of the targeted subject visit at each site for Month 4 and after at least 50% of patient study participant visits at Month 12.
- c. Facilitation calls will continue during the enrollment period until the last enrolled subject achieves their Month 6 study visit.

13.2.1.3. Schedule of Activities Table for Patient Study Participants (Long Term Follow Up) ^a

Procedures for Long-Term Follow Up ^a	Month 3	Month 6	Month 9	Month 12	WD	Notes
HIV Associated Conditions, AE and SAE Assessments, Con Meds	X	X	X	X	X	Every effort should be made to enter participants into the Long-Term Follow Up if they withdraw from or discontinue the study after receiving at least one dose of CAB LA and / or RPV LA.
HIV-1 RNA	X	X	X	X	X	
 a. The start of the 52-week follow-up period begins the day of the last CAB LA and/or RPV LA dose.
CD4+ cell counts	X	X	X	X	X	
 b. A PK sample for storage should be collected in the event of virologic failure during the LTFU phase
Plasma for Storage	X	X	X	X	X	
 c. Participants who get pregnant while in study will have additional PK samples for CAB and RPV obtained, see Appendix 8
PK Sample for Storage ^{b,c}						
 d. FRP only. U=urine; pregnant participants who remain in the study do not need pregnancy testing during the study, for the duration of their pregnancy
Clinical Chemistry and Hematology	X	X	X	X	X	
 e. FRP should continue to receive counselling on the need to use adequate contraception for the entirety of the Long-Term Follow-Up Period.
Pregnancy Testing ^d	U	U	U	U	U	
 f. Investigators must discuss choice of HAART regimen and timing of initiation with the medical monitor before initiating
Urinalysis				X	X	
PT/PTT/INR				X	X	
Contraception Counselling ^e	X	X	X	X	X	
HAART Dispensation ^f	X	X	X	X	X	

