13.13.4. Study Population Tables

Study Population Tables					
No.	Population	GSK Standard / Example Shell	Title	Programming Notes	Deliverable
Subject Disposition					
1.1.	Safety	ES1	Summary of Subject Disposition for the Subject Conclusion Record	ICH E3, FDAAA, EudraCT	HL, M12, EOS
1.2.	Safety	SD1	Summary of Treatment Status and Reasons for Discontinuation of Study Treatment	ICH E3	M12, EOS
1.3.	Safety	ES4	Summary of Subject Disposition at Each Study Phase	ICH E3 Intervention/Extension phase: status and reason for withdrawal based on date and reason collected in the study treatment discontinuation form. Long term Follow-up: completion/withdrawal based on data collected in the Study Conclusion form.	M12, EOS
1.4.	Safety	ES5	Summary of Reason for Withdrawal at Each Study Phase	FDAAA, EudraCT	HL, M12, EOS
1.5.	Safety	ES11	Summary of Outcome of Adverse Events Which Led to Study Withdrawal/Treatment Discontinuation at Each Study Phase	EudraCT	M12, EOS
1.6.	Screened	ES6	Summary of Screening Status and Reasons for Screen Failure	Journal Requirements	M12, EOS

Study Population Tables					
No.	Population	GSK Standard / Example Shell	Title	Programming Notes	Deliverable
1.7.	Enrolled	NS1	Summary of Number of Subjects by Country and Site ID	EudraCT/Clinical Operations	M12, EOS
1.8.	Screened	NS1	Summary of Number of Subjects by Site Type and Site ID	Replace Country with Site Type Add column for Investigator Name	M12, EOS
Protocol Deviation					
1.9.	Enrolled	DV1	Summary of Important Protocol Deviations	ICH E3	M12, EOS
1.10.	Enrolled	DV1	Summary of Important COVID-19 Related Protocol Deviations	Update the label for the first row to be "ANY IMPORTANT COVID-19 RELATED PROTOCOL DEVIATIONS"	M12, EOS
1.11.	Enrolled	DV1	Summary of Important Non-COVID-19 Protocol Deviations	Update the label for the first row to be "ANY IMPORTANT NON-COVID-19 RELATED PROTOCOL DEVIATIONS"	M12, EOS
1.12.	Enrolled	DV1	Summary of All COVID-19 Protocol Deviations by Site	Update the label for the first row to be "ANY COVID-19 RELATED PROTOCOL DEVIATIONS". Summary for each site and 'Total' across sites.	HL, M12, EOS

Study Population Tables					
No.	Population	GSK Standard / Example Shell	Title	Programming Notes	Deliverable
1.13.	Enrolled	DV1	Summary of All Implementation Protocol Deviations by Site	Update the label for the first row to be "ANY IMPLEMENTATION RELATED PROTOCOL DEVIATIONS" Summary for each site and 'Total' across sites.	HL, M12, EOS
Population Analysed					

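### Snapshot steps 3.2.2.1, 3.2.2.2 and 3.2.2.4 read the withdrawal reason from the Conclusion form, so an AE discontinuation that enters long-term follow-up may match no step

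*SAP*

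**What the plan says.** References are to the amended RAP.

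- **Appendix 9 (13.9), steps 3.2.2.1 and 3.2.2.2** (safety reasons, not COVID-related and COVID-related): "renal toxicity withdrawal criteria, QTc withdrawal criteria etc., as recorded in eCRF Conclusion form".
- **Step 3.2.2.3** (non-safety, not COVID-related): "investigator discretion etc., as recorded in eCRF Treatment Discontinuation Form".
- **Step 3.2.2.4** (non-safety, COVID-related): "closed/terminated, investigator discretion etc., as recorded in eCRF Conclusion Form".
- **Section 13.13.4, programming note to Table 1.3:** "Intervention/Extension phase: status and reason for withdrawal based on date and reason collected in the study treatment discontinuation form", and then "Long term Follow-up: completion/withdrawal based on data collected in the Study Conclusion form".
- **Section 13.4.1, Table 8:** IP discontinuation is handled separately from study conclusion. The study conclusion of anyone with LTFU visits or LTFU antiretrovirals is placed in the LTFU phase.
- **Section 13.2.1.3 (LTFU schedule):** "Every effort should be made to enter participants into the Long-Term Follow Up if they withdraw from or discontinue the study". This applies once at least one injection has been given, and the follow-up runs 52 weeks from the last injection.
- **Appendix 9, examples from FDA guidance:** a patient who stops because of an AE or death before the window is to be counted as discontinued for AE or death, whatever the HIV-1 RNA result.

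**The concern.** The four sub-steps of 3.2.2 are branches of one question: why did this participant withdraw? They should be mutually exclusive and cover every case, which requires that they read the answer from one place. Here three read one form and the fourth reads another, with no reason given.

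The difference matters because the two forms appear to record different events. The treatment discontinuation form records why study treatment stopped. For a participant who goes on to LTFU, the Conclusion form appears to record how LTFU ended. Someone who stopped treatment for an AE may therefore have no AE on the form that the safety steps consult. At stake is whether the AE/death row of the Month 12 Snapshot tables is complete and agrees with the disposition tables.

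**Working it through.** The plan gives no figure of its own here. The check has three parts: a trace of one participant through the algorithm, the timing, and the size.

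**1. Trace.** Take a participant who stops for an AE after the Month 5 injection, enters LTFU, and has no on-treatment viral load in the Month 12 window.

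| Step | Condition | Does this participant match? |
|---|---|---|
| 1, 2 | Non-permitted change of ART before or in the window | Assumed no |
| 3.1 | On-treatment viral load in the window | No |
| 3.2.1 | Still on study, judged by study treatment | No, treatment has stopped |
| 3.2.2.1, 3.2.2.2 | Safety reason on the Conclusion form | Not if that form is blank or gives the LTFU outcome |
| 3.2.2.3 | Non-safety reason on the Treatment Discontinuation Form | No, that form says AE |
| 3.2.2.4 | Non-safety, COVID-related reason on the Conclusion form | Only after a COVID-related exit from LTFU |

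Apart from that last case, no row applies. If steps 3.2.2.1 and 3.2.2.2 read the Treatment Discontinuation Form, the participant falls in the AE/death row, as the guidance examples require.

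**2. Which discontinuations reach step 3.2.2.** Inputs:

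- Month 12 Snapshot window: target day ± 42 (13.3.1, Table 2).
- On-treatment status lasts to the last injection + 35 days (13.4.2, Table 10).
- Assumption: no oral bridging after the last injection, and no earlier start of LTFU antiretrovirals.
- Illustration: Month 1 injection on 7 July 2019, so the Month 12 target is 7 June 2020.

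End of on-treatment time minus window opening = (last injection + 35) − (target − 42) = 77 − (days from last injection to target).

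- Last injection Month 1: 77 − 336 = −259 days
- Month 5: −136 days
- Month 9: 77 − 92 = −15 days
- Month 10: 77 − 61 = +16 days
- Month 12: 77 − 0 = +77 days

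For last injections up to Month 9, on-treatment time ends before the window opens, so step 3.2.2 decides the class. From Month 10 on it overlaps the window and step 3.1 can apply. The split does not depend on the chosen date. Three calendar months are 89 to 92 days, giving −12 to −15; two are 59 to 62 days, giving +15 to +18.

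A full LTFU (52 × 7 = 364 days) ends 364 − 336 = 28 days after the Month 12 target for a last injection at Month 1, and 364 − 92 = 272 days after it for Month 9. A participant who completes LTFU therefore has no completion record at their own Month 12 target. Early enrollees may have one by the database freeze, but Table 1.3 and Table 8 indicate that it would describe LTFU.

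**3. Size.** With N = 115 (section 2.3), each participant is 1/115 = 0.87 percentage points, and three would be 2.61. The plan does not say how many to expect. No branch of 3.2.2 leads to HIV-1 RNA below 50 c/mL, so that proportion in the unimputed Snapshot (Table 2.2) is the same under either form.

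**The case against.** Several points on the other side stand, and they limit the finding.

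- **The eCRF is not shown.** A reader might infer that the Conclusion form certainly lacks the treatment-stop reason. The SAP does not say so. Table 1.3 and Table 8 make it likely, no more.
- **The intended class is clear.** The form name sits in a bracket of examples. Section 13.6.3 and the guidance examples show that AE withdrawals are not meant to count as virologic failures, and the guidance examples name the AE/death class. A programmer following the intent would get it right.
- **Not every AE discontinuation is affected.** Participants who stop in oral lead-in, decline LTFU or die on treatment can have the correct reason on the Conclusion form.
- **A reader might infer that AE stoppers move to the other-reasons or ≥ 50 c/mL rows.** Step 3.2.2.3 is closed to them because their discontinuation form says AE. Only step 3.2.2.4 remains. It needs a COVID-related, non-safety exit before or during Month 12 and, for the ≥ 50 row, also a last on-treatment value of at least 50.
- **A reader might measure the problem by how long after the window LTFU ends, up to 322 days for a last injection at Month 12.** That is the wrong measure. The analysis runs after database freeze (section 3.2), so what counts is the content of the forms then. Late last injections also leave on-treatment time inside the window.
- **A reader might infer that tolerability loss would be under-reported in the study report.** AE discontinuations also appear in Tables 1.2, 1.4, 1.5 and 3.21 and in Listings 2 and 27. The study is descriptive and efficacy is secondary.

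None of this explains why parallel branches use two sources. A pre-specified algorithm should not depend on the programmer setting aside the source that it names.

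**Conclusion.** The defect holds in a limited form. Steps 3.2.2.1, 3.2.2.2 and 3.2.2.4 name a different source from step 3.2.2.3 and from the note to Table 1.3. Followed literally, an injected participant who stops for an AE and enters LTFU may match no Snapshot category. The main exposure is last injections up to Month 9.

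The effect is mainly on the reason rows of Tables 2.1, 2.2 and 2.5, at 0.87 percentage points per participant, and on their agreement with the disposition tables. The proportion below 50 c/mL in the unimputed Snapshot is not affected. A reader might infer that the LOCF-modified proportion must shift, since section 7.1.3 imputes after COVID-related AE discontinuations. The SAP does not state which record triggers the imputation, so that is a possibility only.

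The conclusion assumes that the Conclusion form holds the LTFU outcome for these participants, and that the steps are programmed as written.

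**What to change.** In Appendix 9, steps 3.2.2.1, 3.2.2.2 and 3.2.2.4, cite the eCRF Treatment Discontinuation Form, as step 3.2.2.3 and the note to Table 1.3 do. Add that the Conclusion form is used only where no treatment discontinuation record exists, for example a death on treatment.

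This takes three wording changes and one added sentence. Table 1.3 already relies on the discontinuation form, so no new data are needed, and the Snapshot reason rows would then use the same source as the disposition tables.

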13.10. Appendix 10: AESI identification

SMQ and PT codes based on MedDRA dictionary version 23.0 for the Month 12 analysis.

13.10.1. Hepatic Safety Profile

Medical concept of hepatic failure and hepatitis. Sub- SMQs (1) 'Hepatic failure, fibrosis and cirrhosis and other liver damage-related conditions' and (2) 'Hepatitis, non-infectious', both of parent SMQ 'Hepatic Disorders (SMQ code 20000005)'; only narrow terms selected from sub-SMQs. Some preferred terms, e.g. PT 'hepatitis fulminant' are duplicated.

SMQ: 'Hepatic Disorders'; SMQ Code: 20000005	
Sub-SMQ: 'Hepatic failure, fibrosis and cirrhosis and other liver damage-related conditions'	
Category: A	
Scope: Narrow	
Preferred Term	PT Code
Acquired hepatocerebral degeneration	10080860
Acute hepatic failure	10000804
Acute on chronic liver failure	10077305
Acute yellow liver atrophy	10070815
Ascites	10003445
Asterixis	10003547
Bacterascites	10068547
Biliary cirrhosis	10004659
Biliary fibrosis	10004664
Cardiohepatic syndrome	10082480
Cholestatic liver injury	10067969
Chronic hepatic failure	10057573
Coma hepatic	10010075
Cryptogenic cirrhosis	10063075
Diabetic hepatopathy	10071265
Drug-induced liver injury	10072268
Duodenal varices	10051010

SMQ: 'Hepatic Disorders'; SMQ Code: 20000005	
Sub-SMQ: 'Hepatic failure, fibrosis and cirrhosis and other liver damage-related conditions'	
Category: A	
Scope: Narrow	
Preferred Term	PT Code
Gallbladder varices	10072319
Gastric variceal injection	10076237
Gastric variceal ligation	10076238
Gastric varices	10051012
Gastric varices haemorrhage	10057572
Gastrooesophageal variceal haemorrhage prophylaxis	10066597
Hepatectomy	10061997
Hepatic atrophy	10019637
Hepatic calcification	10065274
Hepatic cirrhosis	10019641
Hepatic encephalopathy	10019660
Hepatic encephalopathy prophylaxis	10066599
Hepatic failure	10019663
Hepatic fibrosis	10019668
Hepatic hydrothorax	10067365
Hepatic infiltration eosinophilic	10064668
Hepatic lesion	10061998
Hepatic necrosis	10019692
Hepatic steato-fibrosis	10077215
Hepatic steatosis	10019708
Hepatitis fulminant	10019772
Hepatobiliary disease	10062000
Hepatocellular foamy cell syndrome	10053244
Hepatocellular injury	10019837
Hepatopulmonary syndrome	10052274

SMQ: 'Hepatic Disorders'; SMQ Code: 20000005	
Sub-SMQ: 'Hepatic failure, fibrosis and cirrhosis and other liver damage-related conditions'	
Category: A	
Scope: Narrow	
Preferred Term	PT Code
Hepatorenal failure	10019845
Hepatorenal syndrome	10019846
Hepatotoxicity	10019851
Immune-mediated cholangitis	10083406
Immune-mediated hepatic disorder	10083521
Intestinal varices	10071502
Intestinal varices haemorrhage	10078058
Liver dialysis	10076640
Liver disorder	10024670
Liver injury	10067125
Liver operation	10062040
Liver transplant	10024714
Lupoid hepatic cirrhosis	10025129
Minimal hepatic encephalopathy	10076204
Mixed liver injury	10066758
Nodular regenerative hyperplasia	10051081
Nonalcoholic fatty liver disease	10082249
Non-alcoholic steatohepatitis	10053219
Non-cirrhotic portal hypertension	10077259
Oedema due to hepatic disease	10049631
Oesophageal varices haemorrhage	10030210
Peripancreatic varices	10073215
Portal fibrosis	10074726
Portal hypertension	10036200
Portal hypertensive colopathy	10079446

SMQ: 'Hepatic Disorders'; SMQ Code: 20000005	
Sub-SMQ: 'Hepatic failure, fibrosis and cirrhosis and other liver damage-related conditions'	
Category: A	
Scope: Narrow	
Preferred Term	PT Code
Portal hypertensive enteropathy	10068923
Portal hypertensive gastropathy	10050897
Portal vein cavernous transformation	10073979
Portal vein dilatation	10073209
Portopulmonary hypertension	10067281
Primary biliary cholangitis	10080429
Regenerative siderotic hepatic nodule	10080679
Renal and liver transplant	10052279
Retrograde portal vein flow	10067338
Reye's syndrome	10039012
Reynold's syndrome	10070953
Splenic varices	10067823
Splenic varices haemorrhage	10068662
Steatohepatitis	10076331
Subacute hepatic failure	10056956
Sugiura procedure	10083010
Varices oesophageal	10056091
Varicose veins of abdominal wall	10072284
White nipple sign	10078438
SMQ: 'Hepatic Disorders'; SMQ Code: 20000005	
Sub-SMQ: 'Hepatitis, non-infectious'	
Category: A	
Scope: Narrow	
Preferred Term	PT Code
Acute graft versus host disease in liver	10066263
Allergic hepatitis	10071198

SMQ: 'Hepatic Disorders'; SMQ Code: 20000005	
Sub-SMQ: 'Hepatic failure, fibrosis and cirrhosis and other liver damage-related conditions'	
Category: A	
Scope: Narrow	
Preferred Term	PT Code
Alloimmune hepatitis	10080576
Autoimmune hepatitis	10003827
Chronic graft versus host disease in liver	10072160
Chronic hepatitis	10008909
Graft versus host disease in liver	10064676
Hepatitis	10019717
Hepatitis acute	10019727
Hepatitis cholestatic	10019754
Hepatitis chronic active	10019755
Hepatitis chronic persistent	10019759
Hepatitis fulminant	10019772
Hepatitis toxic	10019795
Immune-mediated hepatitis	10078962
Ischaemic hepatitis	10023025
Lupus hepatitis	10067737
Non-alcoholic steatohepatitis	10053219
Radiation hepatitis	10051015
Steatohepatitis	10076331

